## **Exclusion criteria**

Patients will be excluded if they are unable to tolerate sublingual microcirculatory flow imaging (e.g., non-intubated patients dependent upon oxygen by facemask, poor mouth opening), receiving an emergent procedure, have an active malignancy, or mitochondrial disorder.

## **Timeline and techniques for data collection**

Data for each subject will be collected at time points outlined in **Error! Reference source not found.** Prior to surgery, baseline biologic samples, microcirculation imaging, and clinical data will be obtained. Repeated measurements will be obtained in the ICU and surgical floor. Long-term clinical outcomes will be recorded at 30-days or upon discharge.

### **Fig 1. Timeline of data collection.**

## **Demographic and resuscitation data**

Demographic values including age, gender, and ethnicity will be recorded. Preoperative risk scores including the STS (Society of Thoracic Surgeons) mortality score and euroSCORE II (European System for Cardiac Operative Risk Evaluation) will be calculated [51,52]. Intraoperative data including cardiopulmonary bypass time, cross clamp time, blood product use, intravenous fluid administration, and vasoactive administration will be recorded. ICU clinical data (hemodynamics, laboratory testing, etc.), resuscitation data (intravenous fluids, vasoactive administration, blood transfusion, etc.), and clinical outcomes (VVFDs, ICU length of stay, hospital LOS, etc.) will be recorded as indicated in **Error! Reference source not found.** Sequential organ failure assessment (SOFA) scores will be calculated prior to surgery (baseline), as well as 24 and 72 hours after surgery.

[figure not shown]

[figure not shown]
Figure 1

### Physiologic and pharmacologic data

Systemic hemodynamic data, perfusion data, and blood gas measurements will be collected upon ICU admission, then hourly during the first 6 hours of postoperative care. Cardiac output (CO), cardiac index (CI), central venous pressure (CVP), pulmonary artery pressure (PAP), and mixed venous oxygen saturation ( $SvO_2$ ) will be monitored continuously using a pulmonary artery catheter (Edwards Lifesciences LLC, Irvine, CA, USA). Arterial blood pressure will be measured using a standard invasive arterial line. Intraoperative and post-operative administration of blood products, intravenous fluids, vasoactive agents (vasopressor and inotropes), and sedatives will be recorded at each time point.

### Incident Dark Field Microscopy

Sublingual microcirculation imaging will be performed using handheld incident dark field (IDF) videomicroscopy (CytoCam, Braedius Medical BV, the Netherlands) at four time points during the enrollment period. Imaging will be performed by the Principal Investigator or trained research personnel. Video sequences are obtained by placing the CytoCam device in the sublingual space and maneuvered so that pressure and motion do not result in image artifact (**Error! Reference source not found.**). A series of successive video clips (3-5 clips of at least 120 frames or 6 seconds in length) should be captured in distinct areas of the sublingual space to account for vessel heterogeneity. Focus and lighting during video capture may be adjusted to optimize image acquisition. Baseline ( $T_{0h}$ ) imaging will be obtained in the preoperative area prior to surgery on the day of the scheduled operation. Repeated measurements will be obtained upon arrival to the ICU (0-2 hours after surgery,  $T_{2h}$ ), during ongoing resuscitation (2-4 hours post-op,  $T_{4h}$ ), and on post-operative day one after recovery ( $T_{24h}$ ).

**Fig 2. A. Experimental setup with patient in supine position during IDF measurement. B. Anatomical sublingual triangle where measurements are obtained.**

#### Analysis of IDF videomicroscopy

Prior to analysis, video quality will be assessed using the 6-factor Massey quality score, which uses a semiquantitative assessment of each video for appropriate illumination, duration, focus, content, stability, and pressure. Only videos with Massey scores of <10 will be included for further analysis [17]. Three videos with the best quality score will be selected for further processing. All IDF images will be coded then analyzed using an offline, dedicated software (Automated Vascular Analysis v3.02, Microvision Medical, The Netherlands). Microvascular flow index (MFI), microcirculatory heterogeneity index (MHI), total vessel density (TVD), proportion of perfused vessels (PPV), and perfused vessel density (PWD). Individual microvessel flow will be scored as 0=no flow, 1=intermittent flow, 2=sluggish flow, or 3=continuous flow. Vessels will be considered perfused if they are scored as either sluggish or continuous flow. To ensure only vessels contributing to tissue gas exchange and metabolism are included, only vessels < 20  $\mu$ m in diameter will be analyzed. This process follows the current standard for microcirculation measurement and analysis [18]. Interobserver variation will be tested periodically in at least 10% of the subject videos to ensure minimal scoring heterogeneity between investigators.

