### **Risk Assessment**

The risks for patients participating in this study are not greater than minimal risk and include those related to 1) blood collection for study measurements and 2) breach of confidentiality.

Since we will limit the volume of blood collection to less than 3 mL/kg or 50 mL and no more than two blood collections in one week, this falls under the provision of "not greater than minimal risk." For any patient whose clinical condition might be adversely affected by removal of the stated blood volume for this study (e.g., patients with significant anemia or compromised cardiac output), we will discuss further limiting the volume of blood withdrawn for research purposes with the patient's attending physician. Any patient concurrently enrolled in another study for who enrollment in this study would mean the combined blood volume collection would exceed IRB regulations will be excluded from participation in this study. Finally, since patients with shock typically undergo multiple blood draws per day and often have central and/or arterial vascular access devices, whenever possible blood sampling for study purposes will be timed with other clinically indicated blood draws or catheter access in order to limit pain from venopuncture, arterial puncture, and access to indwelling vascular catheters. Only caregivers with expertise and training in venopuncture, arterial puncture, or access of indwelling catheters will be permitted to collect blood specimens for this study.

In the rare cases where phlebotomy is performed for study purposes only, attempts will be made to mitigate patient discomfort by using topical anesthetics, such as EMLA. Also, risks will be minimized by limiting the number of attempts to obtain blood to 2 per patient per day and only individuals skilled at performing phlebotomy will be permitted to attempt.

To minimize a potential breach of patient confidentiality, CRFs will be coded with a study ID, all data will be password-protected, and the safeguards to ensure confidentiality as described.

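### Coding of the video clips is mentioned only after quality scoring and best-three selection, and neither step is stated to be masked

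*Combined protocol and SAP*

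**What the plan says.** The section Analysis of IDF videomicroscopy in the combined protocol and SAP gives four steps, in this order:

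1. Scoring: "Prior to analysis, video quality will be assessed using the 6-factor Massey quality score, which uses a semiquantitative assessment of each video". The six factors are illumination, duration, focus, content, stability and pressure.
2. Cutoff: "Only videos with Massey scores of <10 will be included for further analysis".
3. Selection: "Three videos with the best quality score will be selected for further processing".
4. Coding and reading: "All IDF images will be coded then analyzed using an offline, dedicated software".

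The section does not say who scores or selects, what the code conceals, or how equal scores are resolved. It adds a reliability check: "Interobserver variation will be tested periodically in at least 10% of the subject videos". The stated aim of that check is consistent scoring between investigators, and clip selection is not mentioned.

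On acquisition, the section Incident Dark Field Microscopy says "Imaging will be performed by the Principal Investigator or trained research personnel", with three to five clips taken from distinct sublingual areas at each of four time points.

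**The concern.** PVD and MHI are the exposure. Sample size and power splits patients at a PVD of 22 mm/mm², and the hypothesis under Outcome measures combines low PVD with high MHI. Both are computed from the clips that survive scoring and selection. The clips come from different areas precisely because vessels are heterogeneous, so which clips are kept can affect both measures.

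Grading content or pressure on a semiquantitative scale involves judgement. If the grader knows that a clip comes from a patient in shock, or from the early postoperative period, that judgement can lean towards the expected result. Masking only the later software step cannot undo such a lean.

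The setting makes this knowledge plausible. Imaging is done at the bedside, the study team draws central venous gases at the same time (Biological samples), and nothing separates the imagers from the scorers. Sample size and power also allows subjects to be excluded for inadequate video quality, so scoring can affect who is analysed as well as which clips are read.

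**Working it through.** The plan states no figure that tests this point. The check is a reading of the text, followed by a bound on how much selection could matter.

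**Order of steps.** Two orders are explicit: quality scoring comes before analysis, and coding comes before analysis. The order of coding relative to scoring and selection is not stated outright. Read in sequence, coding comes last before the software.

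**Meaning of coded.** The image section does not define it. Under Risk Assessment, "CRFs will be coded with a study ID". Data Collection and Management and the consent text on stored blood samples use the word in the same sense: a study identifier in place of a name. Such a label protects identity. It need not hide time point or shock status, so early coding in that sense alone might not mask the scorer.

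**Masking elsewhere.** No section states that image scoring, selection or reading is masked to patient, time point, clinical state or outcome.

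**Room for choice.** With k usable clips, the number of possible sets of three is C(k,3):

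- k = 3: 1 set, so there is no choice among clips (the below-10 cutoff still applies)
- k = 4: 4 sets
- k = 5: 10 sets

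**Largest average shift from selection.** Suppose, against the stated rule, that selection followed vessel density entirely. Treat clip values within a patient as independent and normal with SD s (assumption).

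- Three of five: the expected values of the lowest three are −1.16, −0.50 and 0.00 in units of s. Their mean is (−1.16 − 0.50 + 0.00)/3 = −0.55. Simulation with 400,000 draws gave −0.552 for the lowest three and +0.555 for the highest three.
- Three of four: the same simulation gave −0.341 and +0.345, so about 0.34 s.
- Three of three: 0.

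**Scale.** The documents give no s. If s lay between 1 and 4 mm/mm² (assumption), the bound would be 0.34 × 1 = 0.34 to 0.34 × 4 = 1.4 mm/mm² for three of four, and 0.55 × 1 = 0.55 to 0.55 × 4 = 2.2 mm/mm² for three of five. It would matter most for patients close to 22 mm/mm².

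**What the bound leaves out.** It covers the choice of three clips for PVD. It does not cover the below-10 pass/fail decision, and it does not quantify any effect on MHI.

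**The case against.** **The order is inferred.** A reader might infer that the plan prescribes selection by unmasked staff before any coding. The text does not go that far. The sequence comes from sentence order, and the phrase about all images could mean that every captured clip is coded first. This stands: the document leaves masking open, and it does not prescribe its absence.

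**Selection is not free choice.** The rule is fixed in advance: a score below 10, then the three best. The six factors are image-quality criteria and vessel density is not among them. This also stands. It confines discretion to grading and to equal scores. How often equal scores would occur cannot be judged, because no score distribution or per-factor scale is given.

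**The scorers' knowledge is not shown.** The imagers are named but the scorers are not. The primary outcome runs to day 30 and the timing of scoring is not given, so knowledge of the outcome cannot be assumed. The point rests only on the absence of any stated safeguard.

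**Safeguards may exist elsewhere.** The section refers to a published consensus standard, and the sample-size section to an S1 Appendix. Neither was available. The interobserver check helps only if it covers scoring and selection, which is not stated.

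**The remedy is partial.** The operator positions the device and adjusts focus and lighting at the bedside, and no coding order can mask that. This is true, but it is no reason to leave the later steps open.

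**Conclusion.** The point holds as a free improvement. As written, coding is mentioned only after quality scoring and clip selection, no masking of either step is stated, and coded in its usual sense in this document need not conceal time point or shock status. A semiquantitative step that feeds the exposure definition is therefore open to bias.

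The possible effect is limited. If selection were driven wholly by density, the average shift would be about 0.34 clip SD for three of four clips and 0.55 for three of five, assuming independent normal clips, and zero when only three are usable. Selection under the stated quality rule should do less.

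A reader might want to turn this bound into a share of patients moved across the PVD cut. The documents do not support that. They give neither a within-patient nor a between-patient SD, and the calculation would require five usable clips and the full shift in the same direction for every subject. No reclassification rate should be claimed. The sample size is unaffected.

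**What to change.** Amend Analysis of IDF videomicroscopy so that:

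- every captured clip receives a random code before quality scoring, and the code hides subject, time point and shock status, not only identity;
- the below-10 cutoff and the best-three selection are applied to coded clips;
- equal quality scores are broken at random or by acquisition order;
- the text says who scores and selects, and that the interobserver check covers quality scoring and selection.

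The section should also acknowledge that bedside acquisition remains unmasked.

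The cost is essentially nil: the coding step moves earlier, with no extra reader and no change to the sample size. If the team already codes clips first, one clarifying sentence on the order and on what the code hides, plus the tie rule, is enough.

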#### Biological samples

Blood gas samples will be drawn into a commercial, pre-heparinized 1 mL blood sampler then immediately analyzed by an ABL90 FLEX automatic blood gas analyzer (Radiometer America Inc., Brea, California, USA). Arterial blood gas samples will be obtained by clinical staff every 1-2 hours for the first 6 hours after ICU admission based on current clinical practice. Central venous blood gas measurements will also be obtained by the study team at the time of microcirculation measurement. Hemoglobin, hematocrit, pH, PaO2, PaCO2, and glucose are also reported on each blood gas analysis. After 6 hours, blood gas analysis will be performed as needed by the clinical team. For biomarker and mitochondrial function analysis, enrolled patients will undergo phlebotomy with volumes of 15 mL drawn into K2EDTA tubes. Blood samples will then be centrifuged at room temperature using Ficoll-PaqueTM PLUS (GE) and Leucosep tubes (Greiner Bio-one). Plasma specimens will be stored at -80°C for later evaluation of the mechanisms of microcirculatory dysfunction. Peripheral blood mononuclear cells (PBMCs) will undergo further analysis and processing as detailed below.

#### Mitochondrial respiration

[figure not shown]
A population of PBMCs will be obtained and analyzed from the plasma buffy coat within 1 hour of blood draw. A cell count and viability will be calculated using the Cell Countess II (Invitrogen) with trypan blue exclusion. Between 4-5  $\times$  10^6 PBMCs will be used for respiration analysis and residual PBMCs will be processed and stored

at-80° C for future quantitative PCR. Unless otherwise specified, all reagents will be obtained from Sigma-Aldrich and Invitrogen.

Mitochondrial respiration will be analyzed using an Oroboros O2k-FluoRespirometer (Oroboros Instruments, Innsbruck, Austria) with a substrate-uncoupler-inhibitor titration (SUIT) protocol and MiR05 buffer [19]. The SUIT protocol measures oxidative phosphorylation capacity with electron flow through complex I (CI) and complex II (CI + CII) using malate, pyruvate, glutamate, and flavin adenine dinucleotide-linked substrate succinate in the presence of adenosine diphosphate. The addition of digitonin allows for the measurement of specific complex-linked activity. Oligomycin, an inhibitor of the ATP synthase, uncouples respiration from ATP-synthase activity to measure respiration where the O2 consumption is dependent on the leakiness of the mitochondrial membrane and back-flux of protons into the mitochondrial matrix independent of ATP synthase (LEAKCI+CI). Maximal convergent non-phosphorylating respiration of ETSCI+CI is evaluated by titrating the protonophore, carbonyl cyanide p-(trifluoromethoxy) phenylhydrazone. ETSCI+CI is considered a stress test for mitochondria, a marker of mitochondrial respiratory reserve. Non-phosphorylating respiration specifically through CII (ETSCII) is achieved through the addition of rotenone, an inhibitor of CI. The complex III (CIII) inhibitor antimycin-A is added to measure the residual non-mitochondrial oxygen consumption, and this value is subtracted from each of the measured respiratory states to provide only mitochondrial respiration. Complex IV (CIV)-linked respiration will be measured by the addition of ascorbate with N,N,N,N-tetramethyl-phenylenediamine. The CIV inhibitor sodium azide will be added to reveal the chemical background that is subtracted from the N,N,N,N-tetramethyl-phenylenediamine-induced oxygen consumption rate. Mitochondrial reactive oxygen species production will be measured using the Amplex UltraRed method [20]. All data will be acquired using DatLab 7 (Oroboros Instruments, Innsbruck, Austria) and respiration value will be normalized to cell count.

### Outcome measures

Our hypothesis is that patients with poor post-operative sublingual functional capillary density (defined as a PVD < 22 mm/mm^2 and MHI > 0.4) will have a higher degree of postoperative cardiovascular and pulmonary organ injury compared to patients with normal postoperative microcirculation. The primary outcome for this study will be VVFDs during the first 30 days after surgery. This outcome was chosen because our elective cardiac surgery patients are managed using early recovery after surgery (ERAS) protocols, with a goal to be extubated and weaned off vasopressors within 24 hours after surgery [21,22]. VVFDs will be calculated as a reverse count of consecutive days without requiring ICU-level respiratory or vasopressor support (**Error! Reference source not found.**). Our research group has used a similar primary outcome in a previous clinical trial [23]. The day of operation (day zero) will not be included as all patients undergoing cardiovascular surgery with CPB require mechanical ventilation and vasoactive medications on the day of surgery. Ventilator days will include mechanical ventilation via endotracheal tube or tracheostomy, high-flow nasal cannula  $\geq$  40 liters/minute with an FiO2 > 40%, or non-invasive positive pressure ventilation not prescribed at home. Non-invasive positive pressure ventilation and HFNC will be included as these both require the patient to remain in our ICU. Vasoactives include epinephrine, norepinephrine, vasopressin, phenylephrine, dobutamine, or milrinone at any dose. Subjects in need of respiratory or vasopressor support on day 30, or die before day 30 will be assigned zero VVFDs. If the patient is discharged prior to hospital day 30 a “last status carried forward” approach will be used. Secondary outcomes will include sequential organ failure assessment (SOFA) score on day 1, day 3, diagnosis of acute kidney injury (defined as an increase in serum creatinine  $\geq$  0.3 mg/dL within 2 days), and hospital length of stay.

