## Materials and methods

### Study objective

The primary objective of the MicroRESUS study is to evaluate the microcirculatory and mitochondrial function in patients following elective cardiovascular surgery with cardiopulmonary bypass, to determine if these parameters outperform traditional biomarkers and global hemodynamic measurements to predict clinical outcomes.

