## **Sample size and power**

Using data from our previous foundational work as well as unpublished pilot data, we anticipate a 1:1 allocation of patients to the high ( $PVD > 22\text{mm/mm}^2$ ) and low group ( $PVD \leq 22\text{ mm/mm}^2$ ). We will need a sample size of at least 134 subjects to detect at least a 2-day difference in ventilator and vasopressor-free days (VVFDs) with a  $\beta=0.8$ , using a one-sided t-test  $\alpha=0.05$  [5,6]. We will enroll a total of 140 subjects to allow for a 5% loss to follow-up (surgical delay, ICU delay, cancelled surgery, etc.) and exclusion due inadequate microcirculation video quality (S1 Appendix).

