### Statistical and analysis plans

Continuous variables characterizing demographical data, microcirculation data, and mitochondrial respiration measurements, and outcomes data will be reported as means with standard deviations if normally distributed or medians with interquartile ranges if not normally distributed. Categorical variables will be represented as frequencies and proportions. To examine the predictive performance of selected variables for the primary outcome, we will construct receiver operator characteristic curves for threshold values of PVD, MHI, lactate,  $SvO_2$ , mean arterial pressure, and cardiac index. A Youden index will be calculated to determine the best cutoff value for determining prolonged VVFDs.

Linear regression modeling will be used to examine the relationship between L/P ratio and postoperative microcirculation variables. We will perform univariate analyses on candidate predictor variables of L/P ratio including PVD, MHI, LFTs, creatinine, CPB time, cross clamp time, and catecholamine administration. Multiple linear regression analysis will be used to model the effect of significant predictors. Repeated measure ANOVA will be used to compare changes in microcirculatory variables, mitochondrial respiration, and mitochondrial reactive oxygen species production over time. To adjust for multiple comparisons, post-hoc pairwise Tukey Kramer t-tests will be performed. All analyses will use statistical software (SAS version 15.1, Cary, NC; Prism v 9.0, Graph-Pad Software, San Diego, CA).

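### The sample size rests on a PVD-only split, the hypothesis uses a joint PVD and MHI group, and the analysis section compares VVFDs between neither pair of groups

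*Combined protocol and SAP*

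**What the plan says.** Three sections of the combined protocol and SAP bear on the primary comparison.

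- **Sample size and power.** The text reads "we anticipate a 1:1 allocation of patients to the high" PVD group (above 22 mm/mm²) and the low group (22 or below). At least 134 subjects are needed to detect a 2-day VVFD difference, "using a one-sided t-test" at α = 0.05 with β written as 0.8. MHI is not mentioned.
- **Outcome measures.** The hypothesis concerns "patients with poor post-operative sublingual functional capillary density (defined as a PVD < 22 mm/mm 2 and MHI > 0.4"; these patients are expected to have more organ injury "compared to patients with normal postoperative microcirculation". No cut-offs for normal are given. VVFDs over 30 days are the primary outcome.
- **Statistical and analysis plans.** For VVFDs, beyond descriptive summaries, the plan is "we will construct receiver operator characteristic curves for threshold values of PVD, MHI, lactate" and three haemodynamic variables, followed by "A Youden index will be calculated to determine the best cutoff value for determining prolonged VVFDs". The regressions model the lactate-to-pyruvate ratio. The repeated-measures ANOVA and its pairwise tests concern changes over time in microcirculatory and mitochondrial measures.

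The Study objective is predictive: "to determine if these parameters outperform traditional biomarkers and global hemodynamic measurements to predict clinical outcomes". On timing, the Incident Dark Field Microscopy section says "Repeated measurements will be obtained upon arrival to the ICU" (T2h), during resuscitation (T4h) and on post-operative day one (T24h). The supplied text names none of these as the image that classifies a patient.

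**The concern.** Sizing, hypothesis and analysis should describe one contrast; here they do not. The sizing contrast uses one variable, the hypothesis uses two, and the analysis section tests neither grouping. A patient with low PVD but MHI of 0.4 or less, or with high MHI but adequate PVD, is placed by the sizing rule but has no stated place under the hypothesis.

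At stake is the pre-specification of the main inference. The grouping, the handling of discordant patients, the classifying image and the test could each be settled late. The Status and timeline section plans a preliminary analysis of images and VVFDs in 2022 while enrolment continues, so the choice could be made after outcomes have been seen. The documents do not say that this will happen; nothing in them prevents it.

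**Working it through.** **1. The definitions side by side**

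| Element | Sample size and power | Outcome measures | Statistical and analysis plans |
|---|---|---|---|
| Exposed group | PVD ≤ 22 | PVD < 22 and MHI > 0.4 | PVD and MHI taken separately, no cut-offs stated |
| Comparator | PVD > 22 | Normal, no numbers | None |
| VVFD comparison | One-sided t-test | Not named | ROC curves and Youden index only |

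A PVD of exactly 22 also changes group between the first two columns. That affects only ties and is minor. The added MHI condition is the real difference.

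**2. The 1:1 split**

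The joint group is a subset of the low-PVD group. If half of patients have low PVD and a fraction q of those also have MHI > 0.4, the joint share is 0.5 × q. It reaches 50% only when q is essentially 1.

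**3. The plan's own figure**

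The VVFD standard deviation is not in the supplied text, so 134 cannot be reproduced directly. Reading β = 0.8 as 80% power, I solved for the SD that makes 134 correct.

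- Power = P(T > t₀.₉₅,df), where T is noncentral t with df = n₁ + n₂ − 2 and noncentrality Δ / [SD × √(1/n₁ + 1/n₂)].
- With n₁ = n₂ = 67, Δ = 2 and power 0.80, SD = 4.63 days (standardised difference 2/4.632 = 0.432).
- Check: noncentrality = 2 / (4.632 × √(2/67)) = 2.50, against a critical value of 1.656; power is 0.80.

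**4. Illustration for the joint contrast, difference held at 2 days**

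The documents do not give q. I assume 80% or 60%, so 67 × 0.8 ≈ 54 or 67 × 0.6 ≈ 40 patients in the joint group. Where discordant patients are dropped, I assume a normal group of equal size (40% or 30% of 134 in each).

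| Comparator | Groups | Power at 2 days | Difference for 80% power | Analysable total for 80% power at 2 days* |
|---|---|---|---|---|
| All others pooled | 54 vs 80 | 79% | 2.04 days | 140 |
| All others pooled | 40 vs 94 | 74% | 2.19 days | 160 |
| Discordant dropped | 54 vs 54 | 72% | 2.23 days | 168 |
| Discordant dropped | 40 vs 40 | 61% | 2.60 days | 224 |

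*In the dropped rows the total counts discordant patients, who are imaged but not compared.

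**5. The opposite case**

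Suppose the 2-day difference for low PVD came entirely from the jointly abnormal patients. The joint difference would then be 2/0.8 = 2.5 days or 2/0.6 = 3.33 days. At the same SD, power is about 92% or 98% with others pooled, and 87% or 94% with discordant patients dropped.

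**The case against.** The strongest reply is that this is one document and that the Sample size and power section already names the outcome, groups, test, sidedness and significance level. On that view there are two fixed rules to reconcile, not an open field. Normal can also be read as everyone who is not poor, which places every patient. And the study is observational with a predictive objective, which the ROC analysis serves.

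Part of this stands. The cut-offs 22 and 0.4 are written down, so the choice of grouping lies mainly between two rules. The ROC analysis does belong to the stated objective. The joint definition has a visible rationale too, since the title of a foundational study in the reference list pairs low PVD with high heterogeneity.

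It does not remove the point. The t-test appears only as a sizing input, and even if taken as the planned analysis it tests PVD alone. Reading normal as all others is possible, but the text does not say so, and that reading still breaks the 1:1 split unless q is near 1. If the ROC analysis is primary, 134 was not derived for it, and the Youden step seeks new cut-offs alongside the two already stated.

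Two cautions also stand. Power under the joint rule could move either way. S1 Appendix and the content of Fig 1 were not supplied; they might name the classifying image or give sizing detail, but would not reconcile the wording of the two sections.

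**Conclusion.** The concern holds and should be fixed. The mismatch between the sizing groups, the hypothesis groups and the listed analyses is plain from the text and needs no assumption.

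Its effect on power is not determined. The illustrative range is 61% to 79% if the difference stays at 2 days, and 87% to 98% if the whole low-PVD effect sits in the joint group. Both ranges rest on the back-solved SD of 4.63 days and on shares that I assumed. The finding is that the stated 80% was not derived for the stated hypothesis; a loss of power has not been shown. Confidence is high on the mismatch, and lower on the missing classifying image, because Fig 1 was not available.

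**What to change.** Use one primary exposure in both Sample size and power and Outcome measures. The simplest is the PVD ≤ 22 against > 22 split on which 134 already rests. Then:

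- List the matching VVFD comparison in Statistical and analysis plans, with its test and sidedness.
- Name the joint PVD and MHI definition as a secondary analysis, and label the Youden cut-offs exploratory. Keep the ROC analysis for the Study objective.
- Name one early image, T2h or T4h, as the classifying image. T24h falls on post-operative day one, when the VVFD count has already begun, because only day zero is excluded.
- Date the change and state whether VVFDs had been examined by then.

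This costs wording changes in the sections named and one secondary table. It needs no new patients or measurements. The drawback is that MHI leaves the primary hypothesis.

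If the joint definition is to stay primary, define normal numerically, assign discordant patients and a PVD of exactly 22, and restate the expected split, the SD and the power at 134. Under the 2-day illustration, 80% power would take 140 or 160 analysable subjects with others pooled, or 168 or 224 with discordant patients dropped. These totals are conditional on the assumptions above and are not a requirement.
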